## **STUDY OBJECTIVES**

**PRIMARY** - The primary objective of this study is to determine if the application of lower frequency (35kHz to 45kHz) ultrasound energy to the waist/abdominal region of the human body is capable of effecting a reduction in the amount of subcutaneous adipose cells and/or tissue to an amount of at least 1 inch and to a statistically significant level. Determination of the reduction in this adipose tissue is achieved via measurement of the body circumference that includes the abdominal area that was treated, and comparing measurements prior to the initial treatment with measurements after the entire treatment regime is concluded. Per the proposed clinical mechanism of action, the disrupted tissue is cleared by the lymphatic system which facilitates excretion or elimination of the disrupted tissue contents. Having been eliminated, the patient should exhibit a reduction in waist circumference. For this objective to be successfully achieved, a reduction in waist circumference of at least one inch must be demonstrated at a point of 12 weeks after the last of three treatment sessions has been applied.

**SECONDARY** - The secondary objective of this study is to assess the safety of this device. Assessment is made by having the patient rate the treatment experience and report any symptoms, side effects, or associated abnormal conditions. Additional assessment is made by the investigators to qualitatively confirm if visually detectable abnormal conditions (example: edema) are presented following the treatment. Success is determined by whether the patients indicate that any discomfort experienced during the treatment, and following the treatment that are directly attributable to the treatment, along with an absence of side-effects or abnormal conditions directly attributable to the treatment, create a risk/benefit condition where the benefit of treatment is regarded to outweigh the risks and temporary discomfort. Quantitatively, the benefit is regarded to outweigh the risk when: 1) No patients report a pain rating of 4 or higher on the Stanford Pain Scale, 2) No patients exhibit any side effects or abnormal conditions at the conclusion of the final treatment, and 3) No patient who was included in the Test group reports that the treatment regimen was unsuccessful.

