### **Study configuration**

This study is designed as a single-arm study. All eligible candidates shall be enrolled to undergo treatment by the device according to the procedure and protocol that are discussed herein. This approach is consistent with other studies that have been done with similar devices where the primary objective of waist circumference reduction was also intended.

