### **Statistical methods planned, including handling data exclusion, analysis of sub-groups if any**

Any patient that did not conclude all three treatments shall be excluded from the analysis. If there are fewer than 37 patients remaining after the study concludes and exclusions are applied, than no analysis shall take place and additional study subject enrolled until a minimum of 40 completed participants exist. In the event that a patient concludes at least one treatment session, but afterwards discontinues

participation in the study, the presence of the patient in the study shall be acknowledged for data analysis purposes. Missing data for such acknowledged participants shall be fulfilled by inserting the least favorable result obtained realized from among all test subjects who did complete the study. Statistical analysis shall then proceed on the fully populated study data.

Primary analysis shall consist of applying the Anova single-factor acceptance test evaluating the change in waist circumference based on the data collected by the tape measure. A confidence of  $P=0.05$  shall be applied. The results of this data shall be directly applied to determining if the primary objective of the study has been met.

A correlation analysis shall be applied to all variable data recorded, as well as key calculations from the data, to identify any potential two-way connections or relationships between sets of data. Any correlations scoring a magnitude of 0.85 or greater shall be discussed and if appropriate, Anova single-factor analysis applied to determine if there is statistical significance to the relationship and any statements that might be supported by the data. Of primary interest is any impact the starting BMI might have on the amount of change, and any impact that gender may impart to the outcome.

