### **Sample size**

A total sample size of a minimum of 40 patients was established for this study. This number is based on

$$n = \frac{2 \cdot (Z_\alpha + Z_\beta)^2 \cdot \sigma^2}{d^2}$$

where:

$Z_\alpha = 1.96$ , based on a confidence of  $P=0.05$  (false rejecting of a true null hypothesis),  
 $Z_\beta = 0.84$ , based on a power of 80% (failure to reject a false null hypothesis),  
 $d = 1.0$  inch reduction in waist circumference as a meaningful/successful change in measurement,  
 $\sigma = 1.50$  inches, based on the evidence presented by a published study under similar treatment parameters and conditions reporting a typical response of 0.75 inches through the umbilical region and assuming some of the population may not respond at all.

The resulting calculation gives a population size of 37. Accounting for possible attrition and adding a generous margin of safety, a recruitment size of 50 individuals is arrived at. Review of the data analysis shall be conducted by an independent entity to confirm the handling and calculation of data, and the conclusions drawn from the data regarding statistical significance.

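### The safety objective turns three zero counts into a favourable risk/benefit verdict with no statement of precision; zero events in 40 treated patients excludes only true rates above 8.8%

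*Combined protocol and SAP*

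**What the plan says.** The protocol's Study Objectives section, under the secondary objective, gives a quantitative test for concluding that benefit outweighs risk. Three conditions are joined by 'and':

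- Pain, with the words that open the rule (the name of the rating scale is cut short here): "Quantitatively, the benefit is regarded to outweigh the risk when: 1) No patients report a pain rating of 4 or higher on the Stanford Pain".
- Effects: "No patients exhibit any side effects or abnormal conditions at the conclusion of the final treatment".
- Perceived success: "No patient who was included in the Test group reports that the treatment regimen was unsuccessful".

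The Introduction says that the analysis will determine success on both the primary and the secondary objectives, so this is a decision rule and not only a summary.

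On numbers, the Sample size section says: "A total sample size of a minimum of 40 patients was established for this study". It adds a margin so that "a recruitment size of 50 individuals is arrived at". The section on planned statistical methods bars analysis at a lower floor: "If there are fewer than 37 patients remaining after the study concludes and exclusions are applied". All the sizing inputs concern waist circumference. The planned analyses are a single-factor ANOVA and correlations. Neither section mentions a safety rate, an interval or a safety analysis.

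The number treated depends on the design. Study configuration says "This study is designed as a single-arm study", whereas the title page and the Synopsis describe a test group and a control.

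**The concern.** Seeing no events is not the same as showing that events are absent or rare. With a few dozen patients, zero observed events is compatible with a true rate of several percent. The rule does not ask anyone to say so; it moves straight from the zero counts to a risk/benefit conclusion.

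This matters because the Objectives and Introduction ask whether the lower frequency brings new or greater risk, and the Adverse Interactions section names possible effects such as pigmentation change and digestive disruption. A bare zero cannot answer that question for effects at a rate of a few percent.

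The third condition does not help here. It concerns whether patients thought the regimen worked, so it carries no information about the rate of harm.

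**Working it through.** **The plan's own figure.** The Sample size formula with its stated inputs gives n = 2 × (1.96 + 0.84)² × 1.50² / 1.0² = 35.28, which rounds up to 36. The plan states 37; the t-based version of the same two-group calculation gives 36.3, which rounds up to 37. The figure is therefore reproduced closely enough. None of its inputs is a safety rate, so it says nothing about safety precision.

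**Inputs for the safety check.**

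- Treated N: 37 (floor for analysis), 40 (minimum sample size), 50 (recruitment).
- N = 20 is an assumption: half of 40, if the two-arm description applies with 1:1 allocation. The documents give no ratio.
- True harm rate p: the documents give none, so 1%, 2% and 3% are assumed.
- Patients are taken as independent, and every occurrence of the harm is assumed to be counted.

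**Formulas.** The chance that no patient shows the harm is (1 − p)^N. The exact two-sided 95% (Clopper-Pearson) upper limit after zero events solves (1 − p)^N = 0.025, so it is 1 − 0.025^(1/N). For N = 40, 1 − 0.025^(1/40) = 8.8%, and 0.99^40 = 0.669.

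| Treated N | Upper limit after 0 events | Unseen, p = 1% | Unseen, p = 2% | Unseen, p = 3% |
|---|---|---|---|---|
| 20 | 16.8% | 81.8% | 66.8% | 54.4% |
| 37 | 9.5% | 68.9% | 47.4% | 32.4% |
| 40 | 8.8% | 66.9% | 44.6% | 29.6% |
| 50 | 7.1% | 60.5% | 36.4% | 21.8% |

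A one-sided 95% limit, 1 − 0.05^(1/N), would be 7.2% at N = 40. The two-sided limit is used throughout, so that the interval and the stated limit agree.

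**From an unseen harm to a passed rule.** The 'unseen' columns concern one harm only. The rule also fails if any other counted event occurs. Suppose other events counted under the first two conditions occur independently with per-patient rate q. The chance of passing those two conditions at N = 40 is then [(1 − p)(1 − q)]^40. The values of q are assumed.

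| Background rate q | Passes, p = 1% | Passes, p = 3% |
|---|---|---|
| 0 | 66.9% | 29.6% |
| 1% | 44.8% | 19.8% |
| 5% | 8.6% | 3.8% |
| 10% | 1.0% | 0.4% |

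The third condition can only lower these chances. So 67% to 30% is reached only if nothing else counted occurs and no Test-group patient reports an unsuccessful regimen.

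**The case against.** The strongest reply is that the rule is already very strict. One mild event fails it. The second condition covers any side effect, and the Adverse Interactions section itself anticipates inflammation, edema and pain. The Sample size section allows that some patients may not respond, so a report of an unsuccessful regimen is plausible. All of this stands. Strictness governs how often the rule passes, however, and not what a pass shows: at N = 40 a pass still excludes only rates above 8.8%.

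A reader might infer that a 1% to 3% harm would be reported as outweighed by benefit in 67% to 30% of studies. The documents do not support that. The three conditions must hold together, so those figures are a ceiling.

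It is also fair to say that no study of this size can rule out a 1% harm. A 95% chance of seeing at least one case needs ln(0.05)/ln(0.99), or 299 patients. That stands, and it is why the remedy is wording and intervals rather than more patients.

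Nor do the documents support an inference that the report would conceal the evidence. Effects are recorded, followed up and audited, and the analysis is independently reviewed. A reader given the counts could work out the interval. What is missing is any requirement that the conclusion respect it.

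Finally, glucose elevation, another listed effect, is a poor example of what could be missed, because patients with diabetes or glucose sensitivity are excluded.

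**Conclusion.** The point holds in a limited form. The secondary objective draws a risk/benefit conclusion that zero counts at the planned size cannot carry, and nothing in the plan states the precision. Zero events in 40 treated patients excludes only true rates above 8.8%; across the plan's own numbers the limit runs from 9.5% (37) to 7.1% (50). It is 16.8% if only 20 are treated.

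The chance that a given harm goes unseen at N = 40, 67% at a 1% rate down to 30% at 3%, rests on assumed rates, independent patients and complete counting. It is an upper bound on a false favourable verdict for a harm that the conditions count. Effects arising outside the time point named in the second condition raise a separate question of capture, which these figures do not address.

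This concerns the interpretation of a secondary objective, not how the study is run, and it should be corrected before enrolment.

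**What to change.** - In the secondary objective and the planned statistical methods, report the number and proportion of patients with a pain rating of 4 or higher, and of patients with each attributable effect. Give each a two-sided 95% Clopper-Pearson interval and use that one convention throughout.
- Take as denominator all patients who started at least one session. A session can be halted for discomfort, and the data-quality and statistical sections leave out patients who stop early (the latter then fills in data for some of them), so a completer denominator could lose relevant patients.
- In the Sample size section, state what zero events excludes at the planned size: rates above 8.8% for 0 of 40 and above 7.1% for 0 of 50. If the two-arm description stands, give the limit for the number actually treated.
- Word the safety conclusion to that limit, and do not conclude that benefit outweighs risk from the zero counts alone.
- Treat the safety objective as descriptive unless the sponsor and investigator justify a maximum acceptable rate before enrolment. Any such rate needs care, because a lenient one could be looser than the present zero-count rule: 1 event in 40 has an upper limit of about 13.2%, so a 15% maximum would let it through.

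The change costs protocol wording and a few exact intervals, with no extra patients, visits or data. The downside for the sponsor is a less favourable safety statement.

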**Efficacy of Low-Frequency, High-Intensity Ultrasound  
for Reduction in Subdermal Adipose Layers**

Device Investigated: Ultimate Contour Body Sculpting Device

Indication Studied: Application of ultrasound for non-invasive waist circumference reduction.

A randomized, blinded comparison of waist circumference reduction of an active test group vs. a placebo control in adults.

Sponsor: CAO Group, Inc.

Protocol ID: 005-00036-8

Development Phase: Performance Validation

NCT ID: Not Yet Assigned

Anticipated Initiation Date: 15 December 2019

Anticipated Completion Date: 1 May 2020

Document Date: 10 October 2019

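### Condition 2 of the safety rule drops the attribution limit in the objective it decides, so one unrelated abnormal condition fails the objective; if a control group is kept, conditions 1 and 2 also count its patients

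*Combined protocol and SAP*

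**What the plan says.** The Secondary paragraph of Study Objectives states the safety objective twice. A narrative sentence first says what success means. It covers "any discomfort experienced during the treatment, and following the treatment that are directly attributable to the treatment", and then continues "along with an absence of side-effects or abnormal conditions directly attributable to the treatment". A second sentence turns this into a quantitative rule with three conditions, all of which must hold:

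- Condition 1, on pain, requires that nobody gives a score of 4 or more on the Stanford scale.
- Condition 2, on effects found by the end of treatment, reads "2) No patients exhibit any side effects or abnormal conditions at the conclusion of the final treatment".
- Condition 3, on the patient's own view of the result, reads "3) No patient who was included in the Test group reports that the treatment regimen was unsuccessful".

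Only the third condition names a group. None of the three repeats the limit on cause.

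The documents disagree on whether there is a second group. The title page announces a "comparison of waist circumference reduction of an active test group vs. a placebo control in adults". Statistical Methods in the Synopsis compares test with control, and Sequence and duration of study period refers to an assigned study group. Study configuration says the study is single-arm and every eligible candidate is treated with the device.

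**The concern.** A pass/fail rule should count the events that its objective counts. Here the objective excludes findings not caused by the treatment, while condition 2 includes them. Because the rule tolerates no events at all, one unrelated finding in one patient is enough to fail it. The sponsor would then have to report failure on an event that its own objective sets aside, or reinterpret the rule after seeing the data.

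If a control group exists, there is a further problem of population. Its patients are counted under conditions 1 and 2, so the group that should show the background level of events could only count against the device.

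**Working it through.** **Step 1: the texts side by side.**

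| | Whose events | Limit on cause |
|---|---|---|
| Defining sentence, side effects and abnormal conditions | not stated | yes, directly attributable |
| Defining sentence, discomfort | not stated | yes for discomfort after treatment; unclear for discomfort during it |
| Condition 1 (pain) | all patients | none stated, but the score concerns the treatment session |
| Condition 2 (side effects, abnormal conditions) | all patients | none |
| Condition 3 (unsuccessful treatment) | Test group | not relevant |

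The contradiction on cause lies between the first and fourth rows. The contrast in population is between conditions 1 and 2 on one side and condition 3 on the other.

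**Step 2: does another section restore the limit?** Post-Treatment Assessment records anticipated effects and sends unanticipated ones to the Adverse Event form; the protocol text describes no judgement of cause there. The diary reviews before treatments 2 and 3 and at follow-up pick out items that may be relevant to treatment, but are not linked to the success rule. Adverse Interactions has the principal investigator assess events in order to decide on the study or the participant, not to attribute cause for condition 2. No section restores either limit.

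**Step 3: consequence under each design.** In a single-arm study every patient is a treated patient, so the group mismatch has no effect; the missing limit on cause remains. In a controlled study that gap also remains, and a control patient's event counts under conditions 1 and 2.

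**Step 4: illustration of size.** The plan states no figure for the safety rule. Its only calculation, under Sample size, concerns efficacy: 2 × (1.96 + 0.84)² × 1.50² / 1.0² = 35.28, or 36 rounded up; the t-distribution version gives 36.3, rounded up to the stated 37. It has no bearing on safety. Only the minimum of 40 completers is used here.

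Inputs:
- n = 40 completers (Sample size); n = 20 control completers, assuming 1:1 allocation of those 40.
- q = chance per patient of an unrelated event that the rule would count. The documents give none; 0.5% to 5% is assumed.
- Patients are taken as independent with the same q.

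Chance of at least one such event: P = 1 − (1 − q)^n.

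| q (assumed) | n = 40, single-arm | n = 20, control group |
|---|---|---|
| 0.5% | 18% | 10% |
| 1% | 1 − 0.99^40 = 33% | 1 − 0.99^20 = 18% |
| 2% | 1 − 0.98^40 = 55% | 1 − 0.98^20 = 33% |
| 5% | 1 − 0.95^40 = 87% | 1 − 0.95^20 = 64% |

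**Step 5: these are not added failure risks.** If events that properly count already fail the rule with probability F, unrelated events add (1 − F) × P. At an assumed F of 90%, the 33% becomes about 3% and the 18% about 2%.

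**The case against.** The strongest reply is that the numbered conditions put figures on the sentence just before them and so inherit its limit. The term side effects already implies a cause, Post-Treatment Assessment looks at the treated area, and the exclusion criteria remove patients with compromised or diseased skin there. This narrows the gap without closing it. The term abnormal conditions carries no cause, condition 2 adds the word any, and the Safety section also collects patients' observations on systemic health. A rule meant to be quantitative should not depend on inheritance by inference. Screening may lower q, but even 0.5% gives 18% in 40 patients.

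Three stronger readings are tempting and are not supported:

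- A reader might infer that a placebo patient's event will fail the device. That needs a control group, which Study configuration rules out. Nor does any section say what a placebo patient would receive, so statements about the energy delivered or the skin reactions to expect in that group would be conjecture.
- A reader might infer that condition 1 also counts pain from any cause. The score is the overall pain during the treatment, so it is already tied to the session. The attribution phrase for discomfort may cover only the period after treatment, so condition 1 need not contradict the objective on cause. Its only gap is the group.
- A reader might take the percentages as added risk of failure. Adverse Interactions anticipates inflammation, edema and pain from the treatment itself, so treated patients may trigger the rule anyway.

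It is also fair to say that an attribution filter loosens a safety test and brings in judgement. That stands as a cost. However, the filter is the protocol's own, taken from the sentence that defines success.

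**Conclusion.** Wrong as written, within limits. Condition 2 contradicts the sentence it is meant to quantify, and followed literally it fails the objective on one unrelated abnormal condition in any patient at the final session. This holds under either design and rests on the text alone. The missing Test-group limit in conditions 1 and 2 is a real defect only if a control group is kept; under the single-arm text it has no effect.

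The size is illustrative: 33%, 55% and 87% in 40 single-arm completers, and 18%, 33% and 64% in 20 control completers, for assumed rates of 1%, 2% and 5%. These figures depend on the assumed rates, on independence, on 1:1 allocation for the second set, and on treated patients not having failed the rule already.

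**What to change.** 1. Reconcile the design first, since it decides whether the population limit is needed: the title page, Statistical Methods in the Synopsis and Sequence and duration of study period against Study configuration.
2. In condition 2, carry over the limit from the defining sentence, so that it counts only findings directly attributable to the treatment.
3. If a control group is kept, confine conditions 1 and 2 to the Test group, as condition 3 already is, and tabulate the control group's events beside them.
4. Record attribution for each event before the waist analysis, and name who judges it. Where a control exists, that person should be blind to group; the protocol does not describe the principal investigator as blinded.
5. List all-cause events in full for all patients, whatever the attribution.

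The cost is wording in one paragraph, an attribution entry per event if the forms lack one, and one table if a control is kept. No new visits or measurements are needed. The downside is that attribution takes judgement; the all-cause listing keeps that judgement visible. The pain threshold and the zero-event standard are left as they are.

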**Post-Treatment Assessment (approximately 15 minutes):**

- The Post-Treatment assessing investigator observes the treated area for any redness, edema, swelling, or other indications specifically called for in the Anticipated Effects treatment record. The patient is asked for any unexpected sensations, for example sensations of high heat or of a "pins and needles" tingling effect in the tissue. These anticipated effects are documented in the treatment session record. Un-anticipated effects are recorded in the Adverse Event form.
- The patient is presented with the Stanford Pain Scale chart and asked to rate their overall pain and discomfort during the treatment. This is documented in the treatment session record.
- A waist circumference measurement of the abdominal region is made using the constant-tension tape measure. This measurement is recorded in the Post-Treatment Measurement record.
- The patient is provided with a study diary form, and instructed to document in the diary any unusual sensations, events, or bodily responses and to bring the form with them for the next visit.
- At the final treatment session only, the patient is provided with the Q-Post Survey to fill out.
- The patient is then scheduled for the next study session, and then excused.

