#### **ADVERSE INTERACTIONS**

Anticipated adverse responses include:

- Localized inflammation, edema, and elevated temperature of the treatment area: Based on the proposed mechanism of action, the application of ultrasound and the disruption of cells could result in a localized increase in tissue temperature, accompanied by increased blood circulation through the insulted tissue.
- Localized pain or discomfort: The action of ultrasound of this frequency and intensity on nerve cells is not well understood. The same mechanism of action could trigger nervous cell responses interpreted by the brain as a pain response. The disruption and cavitation of adjacent adipose cells could also trigger a pain response.
- Possible system disruption: The applied ultrasound energy is intended to provide localized energy at the typical depth of tissue where sub-dermal adipose cells are found. The ultrasound energy could continue to propagate further into the body, reaching gastro-intestinal organs beneath the treated area. In generalized terms, there could be disruptions to digestive processes resulting from exposure to the ultrasound energy.

- Possible elevation of blood glucose levels: The disruption and lysis of adipose cells may release an increased amount of glycogen into the blood stream. Patients who present with diabetes or pre-diabetes or who are susceptible to variations in blood glucose levels may experience side-effects consistent with elevated glucose levels wherein they are unable to metabolize and/or process the glucose products adequately.
- Possible pigmentation changes of the skin: The action of ultrasound on the skin may alter the amount or chemical nature of pigments in the skin, causing discolorations relative to the surrounding skin.
- Possible aggravation of surgically compromised or wounded tissue: The action of ultrasound on tissue that has been disrupted, such as through surgical procedures, previous wounds, or previously or presently inflamed tissue, could create mechanical stresses on the wound boundaries and possible overcome connective tissues across the wound boundaries, resulting in re-opened or inflamed sites.

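### Safety condition 2 fails on any side effect in any one patient at the end of the final treatment, although the plan itself foresees local inflammation, edema and warmth and does not say which effects should count

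*Combined protocol and SAP*

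**What the plan says.** All references are to the combined protocol and SAP.

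- **Study Objectives, Secondary.** The quantitative safety rule, whose pain ratings use the Stanford scale, opens "Quantitatively, the benefit is regarded to outweigh the risk when: 1) No patients report a pain rating of 4 or higher". Condition 2 is "No patients exhibit any side effects or abnormal conditions at the conclusion of the final treatment". Condition 3 is that nobody in the Test group calls the regimen unsuccessful. The three are joined by an and, so all must hold.
- **Same section, narrative part.** Investigators are to confirm whether "visually detectable abnormal conditions (example: edema) are presented following the treatment". The narrative criterion speaks of an "absence of side-effects or abnormal conditions directly attributable to the treatment", and the stated aim is to judge whether benefit outweighs risk and temporary discomfort.
- **Adverse Interactions.** The first anticipated response is "Localized inflammation, edema, and elevated temperature of the treatment area". The reason given is that "the application of ultrasound and the disruption of cells could result in a localized increase in tissue temperature".
- **Post-Treatment Assessment.** In a check of about 15 minutes after each session, the assessor "observes the treated area for any redness, edema, swelling, or other indications specifically called for in the Anticipated Effects treatment record". Anticipated effects go into the session record, whereas "Un-anticipated effects are recorded in the Adverse Event form".

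**The concern.** Condition 2 is meant to put a number on a benefit-risk judgement, but it does not distinguish a mild reddening from a serious injury. It ignores whether the effect was foreseen, how severe it was and whether it cleared. The plan already records anticipated and un-anticipated effects separately, and follows events to resolution in the Follow-up and Monitoring sections. The success rule uses neither piece of information.

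Two things are at stake. Applied literally, a single minor local reaction fails the safety objective and says little about meaningful risk. If such a reaction does occur, there will be pressure to decide after seeing the data that it was not really a side effect, and the sponsor performs the analysis. In the opposite case, a count of zero in a study this small could be read as absence of risk, which it cannot show.

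**Working it through.** **Step 1. Does the rule cover the foreseen reaction?** Edema is the objective's own example of an abnormal condition, an anticipated response, and a named item in the post-session check. It is therefore inside condition 2. Redness and swelling are also looked for. Warmth is less clear: the check asks about heat sensations, but the text does not show that skin temperature is examined, and the Anticipated Effects form is not reproduced.

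**Step 2. Number of patients.** The plan states no pass probability or event rate for the safety rule; its only related figure is the sample size. Its formula gives 2 × (1.96 + 0.84)² × 1.50² / 1.0² = 2 × 7.84 × 2.25 = 35.28, so 36, against the stated 37. The difference does not matter here. I use 40 (stated minimum), with 37 and 50 (recruitment target) as bounds.

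**Step 3. Chance of meeting condition 2.** Let p be the probability that a patient shows a countable effect at the check after treatment 3, taken as equal and independent across patients. Then P(condition met) = (1 − p)^n. The values of p are assumed.

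| Assumed p | n = 37 | n = 40 | n = 50 |
|---|---|---|---|
| 0.5% | 83.1% | 81.8% | 77.8% |
| 1% | 68.9% | 66.9% | 60.5% |
| 2% | 47.4% | 44.6% | 36.4% |
| 5% | 15.0% | 12.9% | 7.7% |
| 10% | 2.0% | 1.5% | 0.5% |

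**Step 4. Break-even rates.** Failure becomes more likely than not when p exceeds 1 − 0.5^(1/n): 1.86% (n = 37), 1.72% (n = 40), 1.38% (n = 50). For an 80% chance of meeting the condition, p may be at most 1 − 0.8^(1/n): 0.60%, 0.56% and 0.45%.

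**Step 5. What a zero count shows.** With 0 of 40, the exact upper limit is 1 − 0.05^(1/40) = 7.2% (one-sided 95%) or 1 − 0.025^(1/40) = 8.8% (two-sided 95%).

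**Step 6. Sensitivity to the design.** Study Configuration describes a single arm, but the title page and Statistical Methods describe a control group. If only a treated half counted (assumed 18 to 25 patients), the 50% break-even rate would be 3.8% to 2.7%, and failure at p = 10% would have probability 85% to 93%. The picture is the same.

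**The case against.** **The rate is unknown.** A reader might infer that the safety objective is likely to fail on an expected, transient reaction. The documents do not support that. They say only that the effects could occur, give no rate, and nowhere call the inflammation, edema or warmth transient; the word temporary is applied to discomfort. The same anticipated list includes re-opened wound sites and glucose elevation, so anticipated there means foreseeable. At a 1% rate the condition would be met about two times in three. This part of the objection stands, and the probabilities are conditional.

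**Scope and timing.** Nor does every immediate side effect count: reactions after sessions 1 and 2 that have cleared fall outside the rule. The time point could also be read as the end of the treatment course. But the assessment scheduled at that point is the check after treatment 3, which makes the immediate reading the natural one. If a later time was meant, the text needs to say so.

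**Attribution.** The attribution qualifier is in the narrative sentence, not in condition 2. It would not help in any case, because a local reaction caused by the ultrasound is attributable to treatment.

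**A strict rule is the sponsor's choice.** This stands in part. A zero-event rule works against the sponsor and creates no false claim of safety, and a failure under it would follow from the rule as written. The problem is the mismatch with the stated benefit-risk purpose and the opening for reinterpretation.

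**Condition 2 may not be decisive.** Condition 3 could fail on its own, since the Sample Size section allows for some non-responders. True, but that does not make condition 2 coherent.

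**Conclusion.** The point holds as a conflict within the plan. On the natural reading, condition 2 scores a foreseeable local reaction in one patient as failure of the safety objective, with no regard to severity, expectedness or resolution.

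How often this would happen depends on a rate the documents do not give. At n = 40, failure is more likely than not above about 1.7% per patient, nearly certain at 10%, and uncommon at 0.5% or below. These figures assume independent patients with a common rate and the check after treatment 3 as the time point. In the other direction, meeting the condition supports only an upper limit of 7.2% or 8.8%, not absence of effects. It is a secondary objective and the repair is one of wording, but it should be made before enrolment.

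**What to change.** 1. Reconcile condition 2 with the Adverse Interactions and Post-Treatment Assessment sections before enrolment. The sponsor and investigators should state which effects count against success, by attribution, expectedness, severity and resolution, and at which time point.
2. Build the definition on the existing split between the Anticipated Effects record and the Adverse Event form. Do not exempt every listed anticipated effect: the list includes re-opened wounds and glucose elevation, which a blanket exemption would remove whatever their severity.
3. Tabulate all anticipated effects by type, severity and resolution.
4. Report the condition 2 count with an exact 95% upper limit, say whether it is one-sided or two-sided, and word the safety conclusion to that limit.

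The cost is a rewording of the secondary objective and one table, with no new visits or patients. Severity grading would need to be added to the record if the form does not already carry it. The downside for the sponsor is that the safety claim becomes a rate with an upper limit instead of none.
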